8.2.6 Assessment of Sjögren's disease activity

SS disease activity will be assessed with the following measures:

- Clinical Labs
- ESSDAI: This validated disease activity measure reflects clinical events that occurred within 28 days and includes physical findings and laboratory measures.
- Physician Global Assessment (PGA) assess global disease activity

8.2.7 Assessment of Changes in Exocrine Function

Changes in salivary flow will be assessed by measuring whole unstimulated saliva flow (WUS) and glandular parotid and submandibular/sublingual unstimulated and 0.2% citric acid stimulated flow rates.

Changes in lacrimal flow will be measured by Schirmer's test.

8.2.8 Assessment of changes in oral microbiota

Supragingival plaque oral microbiome will be collected from three sites on posterior teeth. Decayed, missing, filled teeth (DMFT) scores and periodontal charting will be procured at plaque collection.

8.2.9 Salivary Gland Ultrasound

An ultrasound of the salivary glands may be done in the SS clinic for research purposes. Changes in ultrasonographic findings will be assessed at baseline and at the study day 168. Salivary gland ultrasound can be used to assess the echogenicity and homogeneity of the salivary glands including the submandibular and parotid glands. Validated scoring criteria will be used to assess ultrasonographic feature parameters.

8.2.10 Participant questionnaires

The following assessments will be utilized to assess participant reported outcomes:

1. EULAR Sjögren's syndrome patient reported index (ESSPRI)
2. 2002 American-European Consensus Group (AECG) Criteria Subjective Symptoms
3. Patient Dry Mouth questionnaire
4. Xerostomia visual analog scale [VAS]
5. Fatigue as measured by FSS
6. PROMIS-57 Profile version 2.0
7. Quality of life by the Short Form 36 (SF36) questionnaire
8. Oral health related quality of life by the OHIP-14.

8.2.11 Clinical Laboratory Assessments

The CLIA certified clinical laboratories at the NIH Clinical Center (Department of Laboratory Medicine) will be the central laboratories for all routine clinical laboratory parameters. A serum or urine pregnancy test will be performed for female participants at screening, as per study efficacy evaluation measures, unless postmenopausal (no menstrual period for 2 years or more), had a previous hysterectomy or removal of the ovaries. Some of the testing may be performed at an outside commercial laboratory for patient convenience. Participants will be asked to complete safety visits and further follow-up will be done under the Pathogenesis and/or Natural History of Sjögren's syndrome Protocol (11-D-0172) and/or by their local physicians. Participants will have blood samples drawn through phlebotomy. The laboratory at the NIH Clinical Center will be the central laboratory for all clinical laboratory parameters. Routine testing for various viral infections, including hepatitis B and C and HIV, will be done, since these viruses have been shown to be a cause of salivary gland dysfunction. A positive test for any of these viruses will

affect healthy subjects' participation in this protocol (5.2). Additional testing for COVID-19 antibodies will be done, since Sjogren's Syndrome patients may be at greater risk for infection with COVID-19. Moreover, COVID-19 is now known to cause a plurality of post-infection complications including local effects on the mouth such as taste loss and dry mouth, as well as systemic affects including malaise, fatigue, and joint pain. These are also common clinical complaints in the study population. Participant's participation will not be affected by the results of these tests, but may be used to clinically contextualize interval changes in symptom severity (ESSDAI) in the event of symptomatic or asymptomatic (unknown) infection

8.3 LABORATORY RESEARCH STUDIES

8.3.1 Mechanistic studies

Mechanistic studies will be conducted to investigate effects of Tofacitinib on intracellular signaling molecules, cytokine expression, circulating immune cell types and autoreactive B cells. Results of these mechanistic studies will be used to compare responses in participants on Tofacitinib versus placebo.

All samples for the mechanistic assays will be collected at baseline or study day 1, prior to treatment, and study days 84, 168, and 196. For unscheduled visits, samples for mechanistic studies may be collected when possible. These assays will be performed in laboratories at the NIH. However, all samples will be processed for immediate use or cryopreserved and stored in freezers located in Building 10 (1N). To reduce confounding from variability between multiple assays, all of the samples will be treated appropriately, frozen and stored until all samples can be run simultaneously, for each assay, at the end of the study.

The following is a list of the planned mechanistic studies:

- Change in inflammation in the MSG (i.e., focus score), numbers of infiltrating lymphocytes, and the immunophenotypic distribution in the tissues using immunohistochemistry, flow cytometry, and (when tissue is available) single cell RNA sequencing.
- Changes in levels of SS-related autoantibodies (e.g., anti-Ro52, -Ro60, -la, -CCP, -Sm, -TRIM38, -IFN, and others) using LIPS;
- Ligand-induced STAT phosphorylation in circulating T cells and monocytes using phosphoflow assessment of single cells;
- Expression of STAT-related target genes; expression of pro-inflammatory and immunoregulatory cytokines in T cells and monocytes using RNAseq;
- RNA sequencing of MSG to detect dominant pathway alterations including, but not limited to inflammatory (e.g., “interferon signature”, “granulocyte signature”) and secretory pathways.
- RNAseq in PBMCs to detect dominant pathway alterations including, but not limited to inflammatory pathways (like “interferon signature”, “granulocyte signature”); measures of CD3+ T cell expression of IFN regulatory factor-related genes using RNAseq;

Abbreviated Title: Tofacitinib in Sjögren's syndrome

Version Date: 07/01/2024

- Alteration in peripheral blood immune cell populations with special attention to CD4+, CD25+, Foxp3+ regulatory subsets, and Th17 cells.
- Measures of serum cytokines (IL-2, 4, 6, 7, 9, 12, 15, 17, 23, TNFa, TNFb, IFN α and IFN γ);
- Measurement of cholesterol efflux capacity and NMR lipoprotein profile (particle size and number) and insulin resistance.
- Changes in vascular function, as assessed by the reactive hyperemia index (RHI) using Endopat device, and arterial stiffness using cardio-ankle vascular index (CAVI). Both are surrogate markers of vascular damage and future atherosclerosis development which are amenable to change within this duration of treatment.

Additional biomarker studies: Unused biological samples from above (e.g., whole blood, plasma, serum, and saliva) from the planned mechanistic studies will be frozen and stored for future use. Consent for storage is addressed in informed consent document.

8.4 BIOSPECIMEN EVALUATIONS

Research samples will be collected and stored in locked secure freezers in Building 10 and Building 50 on the NIH campus. Only study investigators and participating research personnel will have access to the samples. Samples will be kept indefinitely unless there is a significant justification for destroying them. The PI will report the loss or destruction of samples collected under this protocol to the Institutional Review Board (IRB).

All samples will be coded and will not have personal identifiers. The codes for identifiers will be contained in a secure, password protected, electronic database (Clinical Trials Data Base (CTDB)) and a participant identification log will be maintained in secure research files maintained in secure and locked offices of the research team...

Coded samples may be shared with collaborators within and outside the NIH. Any remaining samples will be stored in the NIDCR or NIAMS locked freezers. Stored samples may be used for studies related to SS or other autoimmune or disorders affecting salivary glands. Approval from the IRB will be obtained prior to any research use of stored samples beyond the scope of this study.

All participant samples will be coded and used for research purposes without sharing identifying information. This information will be stored on password protected computers.

8.4.1 Correlative Studies for Research/Pharmacokinetic Studies: N/A

8.4.2 Samples for Genetic Analysis

Tissues to be collected for possible genetic analyses include: whole blood and/or PBMCs, and minor salivary gland tissues.

Description of the scope of genetic/genomic analysis

These studies may include, but are not limited to, RNA sequencing, epigenetic sequencing analyses, and whole genome sequencing. Specifically, we may conduct the following sequencing analyses:

RNA sequencing (pending tissue availability):

Abbreviated Title: Tofacitinib in Sjögren's syndrome

Version Date: 07/01/2024

- Bulk RNA sequencing of peripheral blood mononuclear cells and minor salivary glands.
- Single cell, single nuclei, or spatial-transcriptomics RNA sequencing of minor salivary glands and peripheral blood mononuclear cells.

Epigenetic sequencing analyses (pending tissue availability):

- ATAC-Sequencing or other epigenetic sequencing techniques on peripheral blood mononuclear cells and minor salivary glands

Whole genome sequencing (WGS):

- WGS of minor salivary gland or peripheral blood mononuclear cells.

Description of how privacy and confidentiality of medical information/biological samples will be maximized

As part of this study, certain genetic studies, such as whole genome, exome, whole transcriptomic, or epigenomic sequencing may be utilized to understand the effect of Tofacitinib in SS. These studies will not be completed until after data lock. Genetic material (DNA, RNA) will be extracted from PBMCs or tissues and used for sequencing (DNA whole genome, RNA whole transcriptome, or other sequencing methodologies). The samples will be de-identified and coded in a password protected database. Data linking individual sequencing results with individual patients will be available to only the PI and co-investigators. De-identified sequencing data may be shared with collaborators through approved NIDCR Data Transfer Agreements (DTA). Genetic material will not be used for other specific but unrelated investigations unless permission is first granted by the NIH IRB as well as the subject.

The expression profile of mRNA and non-coding RNAs may be analyzed from various tissues and body fluids, such as whole blood, blood components, saliva, urine and biopsy samples (e.g., salivary gland biopsies).

NIH's policy for data-sharing for federally funded genome-wide association studies requires that genotypic and phenotypic information from such studies will be made available through the NIH GWAS data repository designated as database of Genotypes and Phenotypes (dbGAP). Only coded de-identified data will be submitted to dbGAP. The data include the results of the GWAS and selected demographic and clinical variables. We anticipate that similar requirements may be put in place in the future for whole genome sequencing/whole transcriptome data, too.

Medical information and biological samples relating to genomic material will follow the same protections as other biospecimens and medical information collected in this study and as outlined in sections 8.4 Biospecimens, 10.1.5 Confidentiality and Privacy and 10.2 Future Use of Stored Specimens and Data. Data related to genomic analysis will be shared in accordance with NIH

Genomic Data Sharing Policy as described in section 10.9.2, Genomic Data Sharing Plan. Whole genome association studies (GWAS), whole genome sequencing, RNA sequencing, and data deposition into dbGaP.

Management of Results

It is not expected that any of the genomic testing would result in a clinically actionable gene variant. The data obtained will be handled with confidentiality. However, if mutation(s) is/are found that seem to cause or contribute to the disease or phenotype under study, we will verify the

Abbreviated Title: Tofacitinib in Sjögren's syndrome

Version Date: 07/01/2024

finding in a CLIA-certified laboratory. After consultation with the IRB the subjects will be informed and instructed that these genetic findings may require further analysis. A medical genetic counselor will be utilized as appropriate to communicate the genetic findings to the subjects.

It is conceivable that during traditional genetic studies we identify genes associated with Sjögren's syndrome which are also associated with other disorders unrelated to Sjögren's syndrome. This information will not be placed in the medical records, nor will it be discussed with subjects unless there is clear scientific evidence that this finding will have a clinically significant impact on the subject's prognosis or treatment. Sequencing may also identify variant genes that increase the subject's risk for other diseases or may have an impact on the prognosis of other diseases. The PI of this protocol (or his/her staff clinician, nurse, or genetic counselor) will be responsible for communicating that result to the participant. It is essential that this communication include a clear message that the absence of such a finding does not confidently exclude the presence of such a mutation and that if there is an indication for specific testing for any of the genes or disorders covered by current ACMGG secondary findings standards.

We will make no attempts to identify any of these variants and will not inform the subjects unless such variants are identified in our association studies of Sjögren's syndrome and there is clear scientific evidence that this finding will have a clinically significant impact on the subject's prognosis or treatment. In that case, we will contact all subjects and inform them that we have identified such a genetic variant in our cohort and ask them if they want to be informed about their individual result. Then, we will provide the data and appropriate counseling to the subjects who wish to be informed. The details of this process (such as the letter to the subjects) will be submitted to the IRB for approval. Since this is an evolving field, it is possible that we will identify sequence variants associated with Sjögren's syndrome, which may have an effect on the subject's treatment and or prognosis but for which there is no consensus in the medical community. In these cases, we will seek guidance from experts in the field (geneticists, ethicists and the appropriate subspecialists) and will provide a plan of action to the IRB based on their recommendations.

8.5 SAFETY AND OTHER ASSESSMENTS

Patient safety will be assessed through clinical assessments and laboratory studies during scheduled follow up visits (SOA), symptom assessment during interim phone calls (SOA), and assessment of AEs.

8.6 ADVERSE EVENTS AND SERIOUS ADVERSE EVENTS

8.6.1 Definition of Adverse Event

Adverse events (AE) are any unfavorable and/or unintended diagnosis, symptom, sign (including an abnormal laboratory finding), syndrome, or disease that occurs during the study, having been either absent at baseline, or if present at baseline, appears to worsen.

Events will be reported as AE's as described in section 8.2.5.

All AEs will be graded for intensity (severity) according to CTCAE version 5.0 and relationship to study drug as described below.

8.6.2 Definition of Serious Adverse Events (SAEs)

An adverse event (AE) or suspected adverse reaction is considered "serious" if, in the view of either the investigator, sponsor, or Pfizer, it results in any of the following outcomes:

- Results in death
- A life-threatening adverse event, (defined as a participant at immediate risk of death at the time of the event; it does not apply to an AE which hypothetically might have caused the death if it were more severe),
- Requires or prolongs hospitalization (i.e. the AE required at least a 24-hour inpatient hospitalization or prolonged a hospitalization beyond the expected length of stay; hospitalizations for elective medical/surgical procedures, scheduled treatments, or routine check-ups are not SAEs by this criterion),
- Results in a congenital anomaly or birth defect (i.e., an adverse outcome in a child or fetus of a Participant exposed to the trial drug prior to conception or during pregnancy),
- Causes a persistent or significant incapacity or substantial disruption of the ability to conduct normal life functions,
- Any other condition that, in the judgment of the investigator, represents a significant hazard or does not meet any of the above serious criteria but may jeopardize the participant and may require medical or surgical intervention to prevent one of the outcomes listed above
- Important medical events that may not result in death, be life-threatening, or require hospitalization may be considered serious when, based upon appropriate medical judgment, they may jeopardize the participant and may require medical or surgical intervention to prevent one of the outcomes listed in this definition. Examples of such medical events include allergic bronchospasm requiring intensive treatment in an emergency room or at home, blood dyscrasias or convulsions that do not result in inpatient hospitalization, or the development of drug dependency or drug abuse.

8.6.3 Medical Events Not Qualifying as Adverse Events or Serious Adverse Events:

Signs and symptoms of pre-existing medical conditions will not be recorded or reported as AEs or SAEs, unless they represent a clinically significant change from the baseline disease status documented at the Pre-screening Visit. In addition, hospitalization for elective procedures or surgeries will not be considered SAEs, nor will inpatient hospitalizations for convenience.

8.6.4 Clinical Laboratory Test Results Not Qualifying as Adverse Events or Serious Adverse Events:

A clinically significant laboratory result that is present at baseline and does not change significantly during the study will not be reported as an AE or SAE. The clinical significance of a change in a laboratory result will be determined by the PI or medically responsible medical investigator.

The PI, along with the medically responsible investigator will evaluate all clinical laboratory and imaging results for clinically significant abnormalities and document the evaluation in the medical record and case report form. A clinically significant laboratory abnormality will be documented as an adverse event using the following criteria:

The abnormality,

- is not already encompassed by a reported adverse event (e.g., elevated AST need not be reported as an AE if Liver Failure has already been reported as an AE).

- is considered clinically significant by the Investigator.
- necessitates study drug dosing modification (i.e., dose reduction, interruption or discontinuation); and/or
- requires a therapeutic intervention (e.g., concomitant medication, blood transfusion or dialysis); and
- is unexplainable by the participant's current and past medical conditions
- is related to a SS flare.
 - A SS flare is any significant worsening of the signs, symptoms, and laboratory test abnormalities associated with SS. Any increase in the ESSDAI index of >3 or more will be considered as a SS flare⁵⁹.

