Ghoreschi et al., have demonstrated, through a series of in vitro cellular assays and in vivo animal models, the range of Tofacitinib's effects on T cell function and inflammatory cytokines³⁸. Tofacitinib inhibits JAK3 dependent γ_c cytokine receptor signaling and other JAK1 dependent cytokine receptor signaling. These blocking effects manifest as decreased production of inflammatory IL-23 dependent Th17 cells. Additionally, Tofacitinib blockade of JAK1 and JAK3 inhibit Th1 and Th2 differentiation and block IL-6 signaling. In an animal model of collagen-induced arthritis, mice experienced a significant reduction in established arthritis within 48 hours of treatment with Tofacitinib. Circulating inflammatory markers decreased within 4 hours, demonstrating a remarkably fast onset of action. These immediate results were not associated with leukocyte depletion. Histologic confirmation of leukocyte depletion took seven (7) days.

Others have demonstrated that treatment of human participants with Tofacitinib for prevention of graft rejection after kidney transplant results in a differential effect of Tofacitinib on T_{reg} cells and Th1 effector cells where the Th1 effector cells proved more susceptible to JAK blockade⁵². These studies have direct implications for the use of JAK inhibition in SS where, similar to the

positive results demonstrated in RA, we predict that inhibition of signaling molecules with broad effects on inflammatory responses will prove to be beneficial.

Tofacitinib likely targets pathogenic inflammatory pathways involved in the development and maintenance of SS. Additional rationale for a Phase Ib-IIa study of Tofacitinib in SS is the exploration of the inhibition of cytokines that may serve a protective role in SS. For example, IL-2 is an important immunoregulatory cytokine that promotes immune response but it is also important for peripheral tolerance⁵³.

IL-2 promotes expression of Foxp3 in regulatory T (T_{reg}) cells. It also inhibits IL-17 production and Bcl6 expression; Bcl6 is important for T_{fh} cells and germinal center formation. Although no evidence exists in mouse models or in humans treated with Tofacitinib that this drug promotes autoimmunity, this remains a theoretical possibility. In addition, Tofacitinib can weakly inhibit JAK2 and thereby interfere with the action of erythropoietin, GM-CSF and IL-7. Consequently, Tofacitinib could theoretically exacerbate the anemia and lymphopenia associated with SS.

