3 OBJECTIVES AND ENDPOINTS

OBJECTIVES	JUSTIFICATION FOR ENDPOINTS	ENDPOINTS
Primary		
To determine the safety and tolerability of Tofacitinib in participants with SS and mild to moderate disease activity.	This is an FDA approved drug that is not currently approved for use in the Sjögren's syndrome population. Tofacitinib has demonstrated both clinical and molecular potential to be an effective treatment for SS, however studies are lacking in this research population.	Safety and tolerability will be measured by assessment of adverse events (AEs) and clinical safety laboratory tests throughout the study. Toxicity is defined as any study drug-related Grade 3 or higher adverse event, as measured by the National Cancer Institute (NCI), Common Terminology Criteria for Adverse Events (CTCAE), Version 5.0).
Secondary		
To assess clinical improvement after treatment with Tofacitinib as measured by no change or improvement in the ESSDAI and no worsening on the physician's global PGA.	The ESSDAI was developed to be used as an outcome measure in clinical trials involving Sjögren's syndrome patient cohorts. It allows for assessment/scoring of major domain activity relevant to a SS population.	Assessments of clinical response will be measured by: 1) the change in ESSDAI between baseline and study day 168 2) No worsening of PGA between baseline and study day 168
To demonstrate that treatment with Tofacitinib is effective clinically and biologically in SS individuals with mild to moderate disease.	Data from a randomized placebo-controlled trial of Tofacitinib in SS would yield evidence to further pursue JAK/STAT pathway targeting in SS. Salivary flow rates are an objective measure of organ	Change in salivary flow rates between baseline and study day 168

OBJECTIVES	JUSTIFICATION FOR ENDPOINTS	ENDPOINTS
	function. Low salivary flow is a primary feature of SS and may be used as a non-invasive measure of therapeutic intervention.	

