8.7.4 Time Period and Frequency for Event Assessment and Follow-Up

The occurrence of an adverse event (AE) or serious adverse event (SAE) may come to the attention of study personnel during study visits and interviews of a study participant presenting for medical care, or upon review by a study monitor.

All AEs including local and systemic reactions not meeting the criteria for SAEs will be captured on the appropriate case report form (CRF). Information to be collected includes event description, time of onset, clinician’s assessment of severity, relationship to study product (assessed only by those with the training and authority to make a diagnosis), and time of resolution/stabilization of the event. All AEs occurring while on study must be documented appropriately regardless of relationship. All AEs will be followed to adequate resolution.

Any medical condition that is present at the time that the participant is screened will be considered as baseline and not reported as an AE. However, if the study participant’s condition deteriorates at any time during the study, it will be recorded as an AE.

The severity of an AE will be documented at its highest level of severity. AEs characterized as intermittent require documentation of onset and duration of each episode.

Any time after informed consent is obtained, AEs and SAEs will be recorded and reported until 7 (for non-serious AEs) or 30 days (for SAEs) after the last day of study participation.

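### Section 8.6.4 makes the cause of a laboratory abnormality a condition for recording it as an adverse event, in conflict with 8.6.1 and 8.7.4

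*Combined protocol and SAP*

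**What the plan says.** The primary endpoint (section 3) has two sources: "Safety and tolerability will be measured by assessment of adverse events (AEs) and clinical safety laboratory tests throughout the study". Toxicity is a drug-related AE of Grade 3 or higher, so it exists only where an AE has been recorded.

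Three sections govern what is recorded:

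- **8.6.1** includes abnormal laboratory findings in the AE definition and sets one test, "having been either absent at baseline, or if present at baseline, appears to worsen". Cause plays no part.
- **8.7.4** says: "All AEs occurring while on study must be documented appropriately regardless of relationship". It also has deterioration of a condition present at screening recorded as an AE.
- **8.6.4** lists criteria for documenting a clinically significant laboratory abnormality as an AE. It must not already be covered by a reported AE, must be judged clinically significant, and must lead to a dosing modification and/or treatment. The treatment bullet ends in a connector: "requires a therapeutic intervention (e.g., concomitant medication, blood transfusion or dialysis); and". The next bullet is "is unexplainable by the participant's current and past medical conditions". The last is "is related to a SS flare", with no connector before it and the definition of an SS flare beneath it.

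Section 8.7.2 then grades relationship to study drug, and allows an event to be possibly related when the participant's own condition may have contributed.

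**The concern.** Every participant has SS, and some will have other conditions that move laboratory values. A rule that records an abnormality only if those conditions cannot explain it settles attribution before 8.7.2 is reached. The abnormalities most exposed are those that could come from either drug or disease, and section 2.3.1 names two: "Tofacitinib could theoretically exacerbate the anemia and lymphopenia associated with SS".

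The condition is not limited to SS. Participants on lipid-lowering drugs may enroll (5.1), and so may those with well-controlled SS-related liver disease (5.2). Section 2.4.1 describes lipid and liver-enzyme rises in Tofacitinib studies.

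At stake are the AE, related-AE and toxicity counts in 9.3.2, and the DSMC alert in 10.7, which needs three or more participants with similar Grade 3 or 4 AEs assessed as related. Investigators also cannot apply the list consistently as printed.

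**Working it through.** The plan states no figure for this point, so there is nothing to reproduce. The check is whether an abnormality explained by disease is recorded under each way of reading the flare bullet.

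**Notation.** A = not already covered by another AE; B = clinically significant; C = dosing modification; D = treatment needed; E = unexplained by existing conditions; F = related to a flare. For the case in question A = B = 1 and E = 0.

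| Reading of 8.6.4 | Rule | With E = 0 | With E = 0 and F = 0 |
|---|---|---|---|
| Flare bullet is a further requirement | A and B and (C or D) and E and F | never recorded | not recorded |
| Flare bullet is an alternative to the whole list | [A and B and (C or D) and E] or F | recorded only if F | not recorded |
| Flare bullet is an alternative to 'unexplainable' only | A and B and (C or D) and (E or F) | recorded only if F and (C or D) | not recorded |

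The first reading contradicts itself, because a change due to an SS flare is explained by a current condition. The other two are coherent, but they record an abnormality explained by disease only if it is labelled a flare. With F = 0 the result is the same in all three, even when C = 1, for example after a dosing interruption for hemoglobin under 6.1.2. Under 8.6.1 the same finding is an AE whenever it is new or worse than baseline.

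**Size per participant.** Target arms are 20 and 10 (4.1):

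- Tofacitinib: 1/20 = 5 percentage points.
- Placebo: 1/10 = 10 percentage points.

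Replacements could enlarge the safety population. If all 41 places were used at 2:1, the arms would be about 41 × 2/3 ≈ 27 and 41 × 1/3 ≈ 14, giving 1/27 = 3.7 and 1/14 = 7.1 points.

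**DSMC alert, for scale only.** Let p be the true proportion of the 20 Tofacitinib participants with a similar, related Grade 3 or 4 laboratory event. The chance of at least three recorded events is P(X ≥ 3), X ~ Binomial(20, p × share recorded). The values of p and the recorded share of one half are assumptions.

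| Assumed p | All recorded | Half recorded |
|---|---|---|
| 5% | 7.5% | 1.3% |
| 10% | 32% | 7.5% |
| 15% | 60% | 19% |
| 20% | 79% | 32% |

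**The case against.** The strongest reply is that the flare bullet must be an alternative, since otherwise no laboratory value could ever qualify. Flare is defined broadly and includes significant worsening of SS-associated laboratory abnormalities. A marked hemoglobin fall in someone with SS anemia might then be called a flare, recorded as an AE, and counted again in the flare row of 9.3.2. Sections 8.6.3 and 8.7.4, and the opening of 8.6.4, also point toward recording significant change from baseline. This stands in part: the list is ambiguous rather than a clean exclusion, and some cases will be caught. But they are caught only by labelling a possible drug effect as disease, and a lipid rise put down to known hyperlipidemia is not a flare. Treating every bullet as sufficient alone would remove the problem, but it ignores the printed 'and' and would let the first bullet qualify anything not already reported.

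The second reply is that nothing is lost from the data. A reader might infer that these events vanish from the primary safety endpoint. The documents do not support that. Laboratory tests are themselves part of the endpoint, 9.2.1 has all safety data listed and summarized, 9.3.1 gives the range as well as the mean, so an extreme value can show, and flares are tabulated separately. What can be lost is the AE, related-AE and toxicity count. No graded or shift analysis of laboratory values is specified to stand in for it.

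Third, a reader might infer that the rule favours Tofacitinib. It applies identically in both blinded arms, so it does so only if the drug causes more abnormalities of this kind. Section 2.3.1 calls the effect theoretical, and the frequencies in 2.4.1 for the first three months in rheumatoid arthritis are low: lymphocytes below 500 in 0.04%, neutrophils below 1000 in 0.07%, and hemoglobin changes no different from placebo. The documents give no basis for assuming a particular number of affected participants, and zero is possible.

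**Conclusion.** The conflict is real. As written, 8.6.4 lets a clinically significant laboratory abnormality that is attributed to an existing condition and not called a flare go unrecorded as an AE, while 8.6.1 and 8.7.4 require it to be recorded. This holds under all three readings of the flare bullet.

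The loss from the AE count follows directly. Loss from the related-AE and toxicity counts, and from the DSMC alert, follows only for events that 8.7.2 would have rated as related; for toxicity and the alert, the grade must also qualify. Each affected participant is worth 5 points on Tofacitinib or 10 on placebo at target size. The number affected is unknown, so no total can be given. The alert probabilities above show sensitivity to assumed rates and do not forecast this trial.

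The trial is descriptive (9.1), so no test or power is at issue. The counts in 9.3.2 are the main primary result, however, and the rule that feeds them should be unambiguous.

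**What to change.** **In 8.6.4:**

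- Remove both the 'unexplainable' bullet and the flare bullet as conditions for recording.
- Join the remaining significance criteria (clinically significant, dosing modification, therapeutic intervention) with 'or'.
- Keep the bullet that avoids double recording of an abnormality already covered by a reported AE.
- Align the rule with the baseline test in 8.6.1.
- Leave drug, flare or other cause to the grading in 8.7.2.
- Move the SS flare definition to a place of its own. It sits beneath the bullet to be removed, and flares are a primary endpoint (9.1).

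**In 9.3.2:** add a by-arm table of worst on-treatment CTCAE laboratory grade against baseline, computed from the laboratory data whether or not an AE was recorded. State which visit is baseline; 9.3.3 uses Day 1. Because this table does not depend on AE recording, it also covers participants already treated.

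**Cost:** protocol wording, one programmed table and somewhat higher laboratory AE counts. No new tests are needed.
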